2.0	15APR2020	Section 6.1: Inclusion criteria 1 removed and changed to COVID-19 diagnosis confirmed by antigen detection test and/or PCR and/or positive serology, or any emerging and validated diagnostic laboratory test for COVID-19 within this period.
		Section 1.5, 6.1: Extra Inclusion criteria: In some patients, it may be impossible to get a confident laboratory confirmation of COVID-19 diagnosis after 24h of hospital admission because viral load is low and/or problems with diagnostic sensitivity. In those cases, in absence of an alternative diagnosis, and with highly suspect bilateral ground glass opacities on recent (<24h) chest-CT scan (confirmed by a radiologist and pulmonary physician as probable COVID-19), a patient can be enrolled as probable COVID-19 infected. In all cases, this needs confirmation by later seroconversion
		Section 10: redefining sampling.due to addition of extra study sites. Section 8.1.5: better definition of duration of treatment Section 13.6: Despite the known safety profile of the study medications and study design, a DSMB is foreseen.
		General: Better definition of progressive disease: Progression to ARDS requiring mechanical ventilation is removed and replaced by: progressive disease requiring mechanical ventilatory support.
		General: Safety follow-up period is 10-20 weeks.
		Section 1.6.1, 8.1.5: Nebulizing is preferably done in an isolation negative pressure chamber, and if not, personnel should use an FFP2 mask. Patient should self-administer the medication and where possible, the room should not be entered within one hour after administration.
		Section 9.4: arterial blood gas mandatory at D1, D6 and FU Section 9.2, 9.4: if arterial blood gas is taken within 24h before first dose administration, as described in point° the arterial blood gas of screening can be used as D1 value
		Section 7.1.2: If a patient decides to leave hospital before day 6 of the study, for example because of clinical improvement, the oxygenation parameters at day of discharge will be used to calculate the primary endpoint measurement.

3.0	14 May 2020	Section 9.4: Schematic overview of the data collection & interventions: lay-out was updated to improve clarity.
		Section 9.4: Added to flowchart, as per standard of care during follow-up visit: 
 - 6 minutes walk test (Section 4.2) - HRCT scan to assess HRCT fibrosis score
		Section 10: 
 - Clarification on study blood sampling added: EDTA only to be collected in selected sites. - processing details of samples were updated from 1500RPM or 410g to 1770 g.
		General: Typo's were corrected.
		General: "requiring invasive mechanical ventilatory support": wording "invasive" changed to "non-invasive / invasive".
		Section 9.2: "on page 36" added to "as described in point".
		Section 9.4: clinical assessments added to flowchart: Ordinal Scale Category, Clinical Sign Sore, NEWS2 Score, SOFA Score, HScore, CURB-65, APACHE II and Glasgow Coma Scale.
		Section 3.2, 4.2: Mean change of SOFA score between day 1 and day 6 or between day 1 and day 11: updated to day 10. Mean change NEWS2 score between day 1 and day 6 or between day 1 and day 11: updated to day 10.
4.0	07 June 2021	General: Typo's were corrected.
4.0	07 June 2021	Section 1.5 and 6.2 -patients on high dose systemic steroids (> 20 mg methylprednisolone or equivalent) Replaced by -patients on high dose systemic steroids (> 20 mg methylprednisolone or equivalent) for COVID-19 unrelated disorder AND - Patients with serum ferritin >2000 mcg/ml (which will exclude ongoing HLH) Replaced by - Patients with serum ferritin >2000 mcg/L (which will exclude ongoing HLH)
4.0	07 June 2021	Section 3.3 and Sections 4.1 and 4.2 Further clarification of Primary and Secondary endpoint measurements
4.0	07 June 2021	Section 4.3: Enumeration and description of planned pharmacodynamic measurements (biomarkers, flow cytometry, immunomonitoring)
4.0	07 June 2021	Section 9.3.6: Clarification on role of VIB-UGent Center for Inflammation Research

		Clarification of which pharmacodynamic parameters, biomarkers, immunomonitoring assays will be performed
4.0	07 June 2021	Definitions of follow-up visit were made consistent.
4.0	07 June 2021	Section 11: Shipment process of optional samples was updated.
4.0	07 June 2021	Section 11.3: Typo selected centres corrected to all centres Better description of sample handling and analysis by centers
	07 June 2021	Section 11.4 Clarification of sample storage and shipment, including role of VIB
4.0	07 June 2021	Section 12.3: correction statistical analysis team Further clarification on statistical analysis performed
4.0	07 June 2021	Section 13.4: Access to data and data ownership better defined
4.0	07 June 2021	Section 14.7: Period of first DSUR reporting modified to 1 year + 60 days

TABLE OF CONTENTS

ICF	=	Informed Consent Form
ICH	=	International Council for Harmonisation
IMP	=	Investigational Medicinal Product
IMPD	=	Investigational Medicinal Product Dossier
LVLS	=	Last Visit, Last Subject
PCWP	=	Pulmonary Capillary Wedge Pressure
PEEP	=	Positive End Expiratory Pressure
PI	=	Principal Investigator
PaO ₂	=	Partial pressure of oxygen
SAE	=	Serious Adverse Event
sHLH	=	secondary hemophagocytic lymphohistiocytosis
SmPC	=	Summary of Product Characteristics
SOP	=	Standard Operating Procedure
SUSAR	=	Suspected Unexpected Serious Adverse Reaction
TERENA	=	Trans-European Research and Education Networking Association
TLC	=	Total Lung Capacity
TLS	=	Transport Layer Security

1. Protocol Summary

SARPAC trial : Use of sargramostim in patients with acute hypoxic respiratory failure due to COVID-19

Title	A prospective, randomized, open-label, interventional study to investigate the efficacy of sargramostim (Leukine®) in improving oxygenation and short- and long-term outcome of COVID-19 patients with acute hypoxic respiratory failure.
Protocol number	SARPAC
Protocol version	V4.0
EudraCT number	2020-001254-22
Sponsor	University Hospital Ghent
Co-ordinating Investigator	[name]
Type of study	Interventional
Fase	IV
Methodology	prospective, randomized, open-label study
Study duration	22 weeks
Purpose of study	To study the effectiveness of additional sargramostim (GM-CSF) inhalation versus standard of care on blood oxygenation in patients with COVID-19 coronavirus infection and acute hypoxic respiratory failure
Number of participants	80
Study population and main inclusion criteria	Patients with confirmed COVID-19 infection and acute hypoxic respiratory failure Presence of hypoxic respiratory failure defined as O ₂ saturation below 93% on minimal 2l/min O ₂ therapy and/or ratio PaO ₂ /FiO ₂ below 350
Investigational drug, dose, route	Sargramostim/Leukine® 125 mcg BID via inhalation, for 5 days Sargramostim/Leukine® 125 mcg/m ² once daily IV upon progression, for 5 days
Treatment duration	5 days, followed by possible 5 day extension upon deterioration

1.1. Protocol specifics

EudraCT number : 2020-001254-22

University Hospital Ghent

1.2. Study Type and Study Phase

This is phase 4 academic, prospective, randomized, open-label, interventional study designed to investigate the efficacy of sargramostim (Leukine®) in improving oxygenation and short- and long-term outcome of COVID-19 patients with acute hypoxic respiratory failure.

1.3. Aim of the study (including primary endpoints)

The **primary objective** is to investigate whether the administration of inhaled sargramostim (Leukine®) at a dose of 250 mcg daily during 5 days improves oxygenation in COVID-19 patients with acute hypoxic respiratory failure.

The **secondary objectives** are:

- to study if early intervention with sargramostim is safe (number of AEs/SAEs)
- to study if early intervention with inhaled sargramostim affects clinical outcome defined by duration of hospital stay, 6-point ordinal scale, clinical sign score, SOFA score, NEWS2 score
- to study if early intervention with sargramostim affects the rate of nosocomial infection
- to study if early intervention with inhaled sargramostim affects progression to mechanical ventilation and/or ARDS
- to study if treatment with sargramostim affects all-cause mortality rate at 4 and 20 weeks post inclusion
- to study if treatment with sargramostim affects features of secondary haemophagocytic lymphohistiocytosis, defined by HS score
- to study if treatment with sargramostim has a favourable effect on long term 10-20 week follow up

1.4. Subjects

1.4.1. Number of subjects

A total of 80 patients with confirmed COVID-19 and acute hypoxic respiratory failure will be enrolled, 40 in the active and 40 in the control group.

1.4.2. Target group

Confirmed COVID-19 patients with acute hypoxic respiratory failure admitted to the COVID-19 isolation ward.

1.5. Inclusion and exclusion criteria

Inclusion criteria

The following patients will be enrolled:

- Recent (≤ 2 weeks prior to randomization) confident diagnosis of COVID-19 confirmed by antigen detection and/or PCR, and/or seroconversion or any other emerging and validated diagnostic test.
- In some patients, it may be impossible to get a confident laboratory confirmation of COVID-19 diagnosis after 24h of hospital admission because viral load is low and/or problems with diagnostic sensitivity. In those cases, in absence of an alternative diagnosis, and with highly suspect bilateral ground glass opacities on recent (< 24 h) chest-CT scan (confirmed by a radiologist and pulmonary physician as probable COVID-19), a patient can be enrolled as probable COVID-19 infected. In all cases, this needs confirmation by later seroconversion.
- Presence of acute hypoxic respiratory failure defined as (either or both)
 - saturation below 93% on minimal 2 l/min O₂
 - PaO₂/FiO₂ below 350
- Admitted to specialized COVID-19 ward
- Age 18-80
- Male or Female
- Willing to provide informed consent

Exclusion criteria

- Patients with known history of serious allergic reactions, including anaphylaxis, to human granulocyte-macrophage colony stimulating factor such as sargramostim, yeast-derived products, or any component of the product.
- mechanical ventilation before start of study
- patients with peripheral white blood cell count above 25.000 per microliter and/or active myeloid malignancy
- patients on high dose systemic steroids (> 20 mg methylprednisolone or equivalent) for COVID-19 unrelated disorder
- patients on lithium carbonate therapy
- Patients enrolled in another investigational drug study
- Pregnant or breastfeeding females (all female subjects regardless of childbearing potential status must have negative pregnancy test at screening)
- Patients with serum ferritin > 2000 mcg/L (which will exclude ongoing HLH)

1.6. Study Interventions

Confirmed or highly suspect COVID-19 patients with acute hypoxic respiratory failure (saturation below 93% on minimal 2 l/min O₂ or PaO₂/FiO₂ < 350) will be randomized to receive sargramostim 125mcg twice daily for 5 days as a nebulized inhalation on top of standard of care (active group), or to receive standard of care treatment (control group). Upon progression of disease requiring initiation of non-invasive or invasive mechanical ventilatory support within the 5 day period, in patients in the active group, inhaled sargramostim will be replaced by intravenous sargramostim 125mcg/m² body surface area once daily until the 5 day period is reached. From day 6 onwards, progressive patients in the active group will have the option to receive an additional 5 days of IV sargramostim, based on the treating physician's assessment. In the control group with progressive disease requiring non-invasive or invasive mechanical ventilatory support, from day 6 onwards, the treating physician will have the option to initiate IV sargramostim 125mcg/m² body surface area once daily for 5 days.

Safety data, including blood leukocyte counts, will be collected in all patients. Efficacy data will also be collected and will include arterial blood gases, oxygenation parameters, need for ventilation, lung compliance, organ function, radiographic changes, ferritin levels, triglyceride levels, etc. as well as occurrence of secondary bacterial infections.

Patients will stop the investigational drug if there is unacceptable toxicity according to investigator's judgement.

1.6.1. IMPs and dosage

LEUKINE® (sargramostim) prepared and administered for inhalation using nebulizer

LEUKINE for injection is a sterile, preservative-free lyophilized powder that requires reconstitution with 2mL normal saline solution. Once reconstituted, LEUKINE can be inhaled as an aqueous aerosol using either a vibrating mesh nebulizer (Philips InnospireGo) or jet nebulizer, per manufacturer instructions. (Nebulizers studied include: AKITA2 Apixneb, PARI LC-Plus set, PulmoAide, Pan LC, Aeroneb Solo Device). Use reconstituted LEUKINE® solution for inhalation within 16 hours following reconstitution and/or dilution.

[figure not shown]
Nebulizing is preferably done in an isolation negative pressure chamber, and if not, personnel should use an FFP2 mask. Patient should self-administer the medication and where possible, the room should not be entered within one hour after administration.

LEUKINE® (sargramostim) prepared and administered intravenously

For patients that are on a mechanical ventilator and cannot be treated with LEUKINE® inhalation:

- The recommended dose is 125 mcg/m²/day administered intravenously over a 4-hour period once daily for up to 5 days.
- For intravenous injection: Administer LEUKINE injection in 0.9% Sodium Chloride Injection, USP. Dilute LEUKINE for intravenous infusion in 0.9% Sodium Chloride Injection, USP. If the final concentration of LEUKINE is below 10 mcg/mL, add Albumin (Human) at a final concentration of 0.1% to the saline prior to addition of LEUKINE to prevent adsorption to the components of the drug delivery system. To obtain a final concentration of 0.1% Albumin (Human), add 1 mg Albumin (Human) per 1 mL 0.9% Sodium Chloride Injection, USP (e.g., use 1 mL 5% Albumin [Human] in 50 mL 0.9% Sodium Chloride Injection, USP).

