8.1.3. Preparation + Dosage + administration of the IMP

For inhalation: LEUKINE® is a sterile, preservative-free lyophilized powder that requires reconstitution with 4mL normal saline solution, to reach a concentration of 62,5 mcg/ml. Once reconstituted, LEUKINE® can be inhaled as an aqueous aerosol using either a vibrating mesh nebulizer or jet nebulizer, aerosolizing 2 ml twice daily. Reconstituted LEUKINE® solution for inhalation should be used within 16 hours following reconstitution and/or dilution. Dosage for inhalation: 125mcg twice daily via nebulizer. Nebulizing is preferably done in an isolation negative pressure chamber, and if not, personnel should use an FFP2 mask. Patient should self-administer the medication and where possible, the room should not be entered within one hour after administration.

For intravenous injection: LEUKINE® injection in 0.9% Sodium Chloride Injection, USP. Dilute LEUKINE® for intravenous infusion in 0.9% Sodium Chloride Injection, USP. If the final concentration of LEUKINE®

is below 10 mcg/mL, add Albumin (Human) at a final concentration of 0.1% to the saline prior to addition of LEUKINE to prevent adsorption to the components of the drug delivery system. To obtain a final concentration of 0.1% Albumin (Human), add 1 mg Albumin (Human) per 1 mL 0.9% Sodium Chloride Injection, USP (e.g., use 1 mL 5% Albumin [Human] in 50 mL 0.9% Sodium Chloride Injection, USP). Once diluted for infusion, LEUKINE® is stable for 6h. Dosage for intravenous injection: 125mcg/m²/day over a 4-hour period for up to 5 days.

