8.1.6. Packaging and Labeling of the IMP

LEUKINE® (sargramostim) for injection is a sterile, preservative-free, white lyophilized powder supplied in a carton containing five 250 mcg single-dose vials.

LEUKINE® (sargramostim) injection is a sterile, clear, colorless solution preserved with 1.1% benzyl alcohol supplied in a carton containing one 500 mcg/mL multiple-dose vial and a carton containing five 500 mcg/mL multiple-dose vials (NDC 0024-5844-05).

Storage and Handling : Leukine should be stored at 4 °C.

Drug will be labeled by Pharmacy UZ Ghent (for UZ Ghent enrolment) for inhaled or intravenous use.

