8.1.7. Storage conditions of the IMP

Store LEUKINE® vials refrigerated at 2°C-8°C (36°F-46°F) in the original carton to protect from light. Do not freeze or shake. Do not use beyond the expiration date printed on the vial.

Leukine® is to be shipped refrigerated at 2°C-8°C (36°F-46°F). The medication will be delivered to the pharmacy of the participating centers. Temperature during shipment and storage is to be monitored continuously. Whenever a temperature deviation occurs, Partner Therapeutics Inc. should be contacted. Partner Therapeutics Inc. might allow further use of the medication vials depending on the duration and intensity of the temperature excursion. The co-ordinating investigator should be informed of this deviation as well.

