On days 1-5, patients in group A will inhale sargramostim 125mcg twice daily for 5 days as a nebulized inhalation using a Philips InnoSpire Go portable mesh nebulizer on top of standard of care. This device is a handheld mesh nebulizer that can be fitted with a facial mask. Patients will be instructed prior to receiving the first dose on how to use this simple device, by a physician. This procedure is finished in 5-10 minutes, and will be performed twice daily, in the morning (between 6 a.m. and 11 a.m.) and evening (between 6 p.m. and 11 p.m.).

Upon progression of disease requiring initiation of non-invasive or invasive mechanical ventilatory support within the 5 day period, in patients in the active group, inhaled sargramostim will be replaced by intravenous sargramostim 125mcg/m² body surface area once daily until the 5 day period is reached. This administration will occur via a centrally placed catheter or peripheral catheter, that will be in place as part of routine medical care at the ICU.

On a final clinical visit between week 10-20 an additional serum tube (5ml) and an EDTA tube (10 ml) will be taken in selected centers.

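### Sections 1.6.1 and 8.1.3 give different reconstitution volumes (2 mL and 4 mL) for the same powder for inhalation; the 8.1.3 instruction is the one shown to fit the planned dose

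*Protocol*

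**What the plan says.** Two sections of the current protocol describe how to prepare the lyophilised powder for inhalation.

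- **Section 1.6.1 (IMPs and dosage, within the Protocol Summary):** the powder "requires reconstitution with 2mL normal saline solution". The solution is to be used "within 16 hours following reconstitution and/or dilution". A figure follows the inhalation text and is not shown in the copy reviewed.
- **Section 8.1.3 (Preparation + Dosage + administration of the IMP):** the powder "requires reconstitution with 4mL normal saline solution, to reach a concentration of 62,5 mcg/ml", and it is given by "aerosolizing 2 ml twice daily". The same section states the dose as 125 mcg twice daily.

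Three other sections bear on the check.

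- **Section 8.1.6:** the powder is "supplied in a carton containing five 250 mcg single-dose vials".
- **Section 1.3:** inhaled sargramostim is given "at a dose of 250 mcg daily during 5 days".
- **Section 9.2:** "patients in group A will inhale sargramostim 125mcg twice daily for 5 days as a nebulized inhalation".

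The amendment history at the front of the protocol records no change of reconstitution volume, so both figures stand as current text.

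**The concern.** The drug, form, route and diluent are the same in both sections, but the volume differs by a factor of two. A twofold difference in volume is a twofold difference in concentration, and the dose a patient receives is concentration times the volume nebulised.

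The risk is that the two instructions get mixed. The protocol text gives one nebulised volume, the 2 mL of 8.1.3, and that equals the reconstitution volume in 1.6.1. Someone who prepares according to 1.6.1 and nebulises the volume in 8.1.3 would give twice the planned dose. Section 8.1.7 says "The medication will be delivered to the pharmacy of the participating centers", so preparation may be handled at several centres, all holding a protocol that prints both volumes. Section 8.1.4 permits no dose adjustments, so a doubled dose would be outside the protocol. The patients have acute hypoxic respiratory failure, and section 8.1.8 lists bronchospasm and dyspnoea among the effects observed with the aerosolised drug.

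**Working it through.** **Inputs**

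| Quantity | Value | Source |
|---|---|---|
| Content of one powder vial | 250 mcg | 8.1.6 |
| Reconstitution volume, summary | 2 mL | 1.6.1 |
| Reconstitution volume, preparation section | 4 mL | 8.1.3 |
| Stated concentration | 62.5 mcg/mL | 8.1.3 |
| Volume nebulised | 2 mL, twice daily | 8.1.3 |
| Planned dose | 125 mcg twice daily (250 mcg per day) | 1.3, 8.1.3, 9.2 |

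**Formulas**

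- concentration = vial content ÷ reconstitution volume
- dose per inhalation = concentration × volume nebulised
- daily dose = 2 × dose per inhalation

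**Step 1: reproduce the figure in 8.1.3**

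- 250 mcg ÷ 4 mL = 62.5 mcg/mL, as stated
- 62.5 mcg/mL × 2 mL = 125 mcg per inhalation, as planned
- 2 × 125 mcg = 250 mcg per day, as in 1.3
- Backwards: 62.5 mcg/mL × 4 mL = 250 mcg, one vial per day

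Section 8.1.3 is therefore complete and agrees with the vial size and with the dose stated elsewhere.

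**Step 2: the volume in 1.6.1**

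- 250 mcg ÷ 2 mL = 125 mcg/mL
- 125 ÷ 62.5 = 2, so the concentration is twice that of 8.1.3 unless more diluent is added

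**Step 3: what the 2 mL preparation delivers, depending on the next step**

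| Next step after reconstitution in 2 mL | Dose per inhalation | Daily dose |
|---|---|---|
| Draw 1 mL undiluted | 125 × 1 = 125 mcg | 250 mcg |
| Add 2 mL diluent (4 mL at 62.5 mcg/mL), nebulise 2 mL | 62.5 × 2 = 125 mcg | 250 mcg |
| Nebulise 2 mL undiluted (volume taken from 8.1.3) | 125 × 2 = 250 mcg | 500 mcg |

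The first two rows give the planned dose and the third gives double. The readable text of 1.6.1 does not say which step follows. The rows show what is possible and say nothing about how likely each is.

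**The case against.** The strongest reply is that the protocol already has a full and correct instruction in the section devoted to preparation. Section 1.6.1 is a summary. Its parent section, 1.6, states 125 mcg twice daily, and the planned dose is the same wherever it appears. A reader who reaches the 2 mL nebulised volume in 8.1.3 has just read that the powder goes into 4 mL, and then reads the 125 mcg dose. The doubled-dose route means taking one number from each section against that context. It would also use two 250 mcg vials a day instead of one, which could be noticed, since the schedule has a drug-compliance row (9.4) and monitoring covers product handling (15.1.3).

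Most of this stands, and it limits the severity. It does not remove the point: a summary may leave out detail, but it should not print a different volume for the same preparation.

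Three stronger readings are tempting, and the documents do not support them.

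- **That 2 mL is an error, or that the protocol plans a doubled dose.** The 2 mL preparation gives 125 mcg if 1 mL is drawn or if it is diluted to 4 mL, and the mention of dilution in 1.6.1 leaves room for the second.
- **That 1.6.1 omits the concentration and the volume to nebulise.** That is true of the readable text only. The figure placed directly after it is not shown and may contain them.
- **That patients received a wrong dose, so past preparation has to be investigated.** Nothing in the protocol shows that any centre worked from 1.6.1.

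**Conclusion.** The mismatch is real: 2 mL in 1.6.1 against 4 mL in 8.1.3, for the same powder and route, in current text. Section 8.1.3 is the version shown to fit the 250 mcg vial and the planned 125 mcg twice daily. The difference amounts to a factor of two in concentration after reconstitution (125 against 62.5 mcg/mL). If the two sections are combined without further dilution, the result is 250 mcg per inhalation and 500 mcg per day in place of 125 mcg and 250 mcg.

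The conclusion assumes that both sections refer to the 250 mcg powder vial of 8.1.6. Section 8.1.3 confirms this for itself by its stated concentration; for 1.6.1 it follows from the description of the product as the same lyophilised powder. The volume conflict itself does not depend on the missing figure.

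Severity is minor. The planned dose is not in doubt, and sample size, endpoints and analysis are untouched. It is still worth correcting, because it concerns preparation of the investigational drug and the correction costs very little.

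**What to change.** After the sponsor and the pharmacy confirm the intended preparation, replace the inhalation preparation text in 1.6.1 with that of 8.1.3: 4 mL normal saline, 62.5 mcg/mL, 2 mL (125 mcg) per inhalation, twice daily. Check that the figure in 1.6.1 agrees. Notify the site pharmacies of the correction.

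The cost is a short text change in one section and one notice to pharmacies. On the evidence in the protocol, a retrospective inquiry at sites is not called for.
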